4.9.1 Analysis of Primary Endpoints

For each of the four target adverse events (DKA, volume depletion, dehydration, serious UTI) the primary endpoints are the incidence rates and times to first occurrence in the index period,

Statistical Analysis Plan (SAP)

Document Date: 17APR2019

Document Version: 1.0 Final

analysed within each PS-based stratum by logistic regression and proportional-hazards Cox regression, respectively. Time to first event occurrence will be compared using hazard ratios and their 95% confidence limits. The assumption of proportional hazards will be tested [Kleinbaum 2012].

Estimates for each stratum and respective variances will be averaged across strata to yield overall weighted estimates considering subclass weights [Austin 2010, Guo 2015].

The statistical analysis models will contain factors and covariates with a potential effect on the outcome. These may include the treatment-confounding candidates listed in section 4.9 above, and will include the season, i.e., the quarter of the calendar year of the index date, and other effects yet to be short-listed. Site may also be included as a candidate variable.

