Data analysis:	
For the incident users of Jardiance® (Empagliflozin) and of DPP4i, analysis will be performed using the “as-treated” (AT) approach. This corresponds to censoring individuals who discontinue use of the index drug, i.e. either switch from the index drug to any other of the index drug Jardiance® (Empagliflozin) or DPP-4 inhibitor during follow-up or stop using the index drug.
 
For the assessment of the primary and secondary objectives, the main data analysis will be conducted in two stages:
 
 - Construction of the propensity score (PS) by modelling the exposure Jardiance® (Empagliflozin) vs. DPP-4 inhibitor - Estimation of the effect of exposure to Jardiance® (Empagliflozin) on the ketoacidosis, severe urinary tract infections, volume depletion and dehydration compared to those exposed to DPP-4 inhibitor. 
Additional sensitivity analyses will be performed to validate the robustness of alternative definitions of outcome, exposure, covariates and reduction of bias due to matching.
 
The following estimates and comparison will be generated:
 
 - Crude and adjusted incidence rates of each of the outcomes among Jardiance® (Empagliflozin) new users and among DPP-4 inhibitor new users. Incidence rates will be reported as point estimates (in cases per 1,000 person-years) and 95% confidence intervals (CIs). - Summary IRRs, after adjusting (via stratified Mantel-Haenszel analysis) for propensity score deciles and calendar year, among Empagliflozin new users versus DPP-4 inhibitor new users - Adjusted IRRs for each of the outcomes will be the main effect estimates of interest. Adjusted incidence rates and IRRs will be calculated by weighting the incidence or IRR of each stratum (defined by propensity score decile and calendar year) by the amount of Jardiance® (Empagliflozin) person-time within the stratum - An additional analysis will further stratify the IRRs by categories of insulin use at the index date - Additional sensitivity analyses will be performed to evaluate potential for bias and confounding. 		

Name of company: [REDACTED]			
Name of finished medicinal product: Jardiance®			
Name of active ingredient: Empagliflozin			
Protocol date: 16 Oct 2017	Study number: 1245.149	Version/Revision: 3.0	Version/Revision date: 23 Sep 2019

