9.7.2 Main analysis using stratification

For the incident users of Empagliflozin along with their respective comparators, analysis will be performed using the “as-treated” (AT) approach. This corresponds to censoring individuals who discontinue use of the index drug, i.e. who either switch from the index drug to any other of the index drugs (Empagliflozin or DPP-4 inhibitor) during follow-up or who stop using the index drug. The AT approach is considering index periods.

For each event of interest, ketoacidosis, severe urinary tract infections, volume depletion, and dehydration, crude and adjusted incidence rates per cohort will be described and compared by means of incidence rate ratios (IRR). Incidence rates will be reported as point estimates and 95% confidence intervals (CIs). Crude incidence rates will be adjusted per 1,000 person-years. Per cohort and, where appropriate per stratum and/or subgroup, the number of person-years is the sum of length of index periods of all patients. Time to first event occurrence will be compared by means of hazard ratios and their 95% confidence intervals.

IRRs and hazard ratios are analysed using stratification. Strata are defined by PS quintiles. IRRs are investigated by means of a stratified Mantel-Haenszel analysis, while hazard ratios are investigated by means of a Cox regression, if proportional hazards can be assumed.

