2.1 Primary objective

The primary objective of this study is to estimate the incidence of

- Ketoacidosis
- Severe urinary tract infections (UTI)
- Volume depletion
- Dehydration

in T2DM patients initiating EMPAGLIFLOZIN compared with the incidence in T2DM patients initiating DPP-4 inhibitors.

The respective primary endpoints are incidences and occurrences of ketoacidosis, severe UTI, volume depletion and dehydration recorded as part of adverse event reporting and encoded according to MedDRA as defined in the Data Management Plan.

Statistical Analysis Plan (SAP)

Document Date: 17APR2019

Document Version: 1.0 Final

[figure not shown]

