4.4 General Principles

All individual collected and derived data will be listed and described per group by means of summary tables presenting frequency counts and percentages for categorical data and arithmetic means, standard deviations, medians, minimum and maximum values for continuous data.

All statistical tests will be conducted with a two-sided significance level alpha of 0.05 and all analyses will be conducted using SAS statistical analysis software version 9.4 (SAS Institute, Inc., Cary, NC) or later.

Baseline (Visit 1) is defined as the last observation on or before the index date.

Let the *index period* define the time from index date to the end of treatment with either EMPAGLIFLOZIN or DPP-4 inhibitor, and the *follow-up period* the time from index date to the end of observation. The *index period during Ramadan* and the *follow-up period during Ramadan*, respectively, are the subperiods of index and follow-up periods, respectively, that will fall in the months of Ramadan as defined in Table 2-1 above, where June 6th 2019 and May 25th 2020 are assumed as the end of Ramadan for the two study years.

Statistical Analysis Plan (SAP)

Document Date: 17APR2019

Document Version: 1.0 Final

Durations of periods, time spans between visits and other times since the index date will be individually derived in days.

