4.6 Statistical Hypotheses

If not otherwise specified, the level of significance is set to 0.05. All statistical tests will compare the treatment groups, EMPAGLIFLOZIN versus DPP-4 inhibitors, for difference. The null hypothesis is of no difference versus the two-sided alternative hypothesis which hypothesizes a difference between groups.

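### SAP 4.9.1 gives each outcome two primary measures and analyses the incidence rate by averaged logistic regression, against the protocol's rate ratio, with no readable rule on which measure leads

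*SAP*

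**What the plan says.** Five places define the primary measure, and they do not agree.

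- **SAP 4.9.1:** for each outcome, "the primary endpoints are the incidence rates and times to first occurrence in the index period". These are "analysed within each PS-based stratum by logistic regression and proportional-hazards Cox regression, respectively". Stratum estimates and variances are then averaged with subclass weights, and the models also carry covariates, including season.
- **SAP 2.1:** "The respective primary endpoints are incidences and occurrences of ketoacidosis, severe UTI, volume depletion and dehydration recorded as part of adverse event reporting". Time to event is not named.
- **Protocol abstract (section 4, Data analysis):** "Adjusted IRRs for each of the outcomes will be the main effect estimates of interest". It describes a Mantel-Haenszel summary over propensity-score (PS) deciles and calendar year, and weighting by empagliflozin person-time.
- **Protocol 9.7.2:** a Mantel-Haenszel IRR over PS quintiles. Beside it, unranked: "Time to first event occurrence will be compared by means of hazard ratios and their 95% confidence intervals".
- **SAP 4.10:** stratified Mantel-Haenszel will be used for incidence rates, as the protocol planned. The text after that sentence is blacked out.

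On testing, SAP 4.4 says "All statistical tests will be conducted with a two-sided significance level alpha of 0.05" and SAP 4.6 says "The null hypothesis is of no difference versus the two-sided alternative hypothesis". Neither singles out a measure.

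**The concern.** A reader of SAP 4.9.1 would programme averaged logistic and Cox fits. A reader of the abstract, protocol 9.7.2 or SAP 4.10 would programme a Mantel-Haenszel IRR. Both could claim to have run the primary analysis.

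The choice matters in two ways:

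- Logistic regression, with no person-time term described, gives an odds ratio. Under as-treated censoring, patients contribute unequal time, so this is not the person-time rate that SAP 4.7.5 defines. If discontinuation differs between groups, the odds ratio moves away from the rate ratio.
- Fitting each stratum separately and averaging fails where a stratum has no event in one group, because that stratum has no finite estimate. Protocol 9.9 itself warns that numbers may be low for ketoacidosis.

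At stake is a safety answer to a regulator whose definition and precision depend on which section is followed.

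**Working it through.** **Plan's own figure.** 750 + 750 = 1,500 patients. The documents give no effect size, power or rate per outcome, so there is no power figure to reproduce. The rates, ratios and discontinuation below are assumptions.

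**1. Odds ratio against rate ratio.** Assumed counts: 26 events in 750 patients over 600 person-years on empagliflozin, and 15 in 750 over 690 on DPP-4 inhibitor.

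- Odds ratio = (26/724)/(15/735) = 1.76. SE of log = √(1/26 + 1/724 + 1/15 + 1/735) = 0.328. 95% CI 0.92 to 3.35, p = 0.085.
- Rate ratio = (26/600)/(15/690) = 1.99. SE of log = √(1/26 + 1/15) = 0.324. 95% CI 1.06 to 3.76, p = 0.033.

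The same events give two answers, and the gap comes from person-time. In simulations (750 per group, five strata, one year, 2,000 runs) with 35% against 15% discontinuing, a stratified odds-ratio test was significant in 36% of studies and the Mantel-Haenszel IRR in 51% (20 per 1,000 person-years, true ratio 2). With 20% discontinuing in both groups the figures were 52% and 53%, so the loss needs unequal discontinuation.

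**2. Strata lost by separate fits.** Assume five strata of 300 patients, empagliflozin shares 0.3, 0.4, 0.5, 0.6 and 0.7, and 0.85 person-years per patient. Empagliflozin person-years P1 are then 76.5, 102, 127.5, 153 and 178.5, and P0 = 255 − P1. With comparator rate λ and true ratio 2:

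P(stratum has events in both groups) = (1 − e^(−2λP1)) × (1 − e^(−λP0))

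- λ = 0.02: 0.926, 0.937, 0.916, 0.868, 0.783. Product 0.540, so 46% of studies lose at least one stratum.
- λ = 0.01: 0.652, 0.682, 0.664, 0.609, 0.520. Product 0.093, so 91%.
- λ = 0.04: 7%. λ = 0.08: 0.3%.

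At λ = 0.02 the expected total is 637.5 × 0.02 × (1 + 2) = 38.25 events, or 7.65 per stratum, before any covariate is fitted.

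**3. Effect on the estimate.** With a and b the events in stratum i and P = P1 + P0:

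- Mantel-Haenszel: IRR = Σ(a·P0/P) / Σ(b·P1/P). The variance of its log is Σ[(a+b)·P1·P0/P²] divided by the product of those two sums.
- Averaged: the mean of log[(a/P1)/(b/P0)] over the k strata with a, b > 0, with variance Σ(1/a + 1/b)/k². Equal weights match the subclass weights of equal-sized quintiles. This treats hazards as constant, so each stratum hazard ratio equals its rate ratio.

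Share of 200,000 simulated studies with |z| > 1.96, true ratio 2:

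| Rate per 1,000 | Mantel-Haenszel | Averaged | Disagree | Only averaged significant |
|---|---|---|---|---|
| 10 | 25% | 3% | 22% | 0.2% |
| 20 | 49% | 31% | 21% | 1.6% |
| 40 | 80% | 77% | 7% | 1.8% |
| 80 | 98% | 98% | 1% | 0.3% |

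Inverse-variance weights give similar disagreement (21.4% at 10 and 22.3% at 20).

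**4. Is it the measure or the pooling?** Replacing the average with one stratified score test, the analogue of a single stratified Cox model, cuts disagreement with Mantel-Haenszel to 3.9%, 1.8%, 0.6% and 0.05%. The loss comes from the averaging.

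**5. False positives.** With a true ratio of 1, at least one of the Mantel-Haenszel and averaged tests is significant in 2.6%, 4.4%, 5.4% and 5.8% of studies at the four rates, against 2.6%, 4.2%, 4.7% and 4.8% for Mantel-Haenszel alone.

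**The case against.** The objective is estimation, no success criterion hangs on p < 0.05, and SAP section 5.1 lists stratified IRR and proportional-hazards tables for every outcome and period, so both results will be shown. The abstract and SAP 4.10 already lean to the Mantel-Haenszel IRR. The unreadable parts of the SAP might hold a rule. All of this stands in part. It limits the harm but does not remove the conflict: SAP 4.9.1 does not carry over the abstract's ranking, and SAP 4.4 and 4.6 do prescribe tests.

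A reader might infer three stronger points that the material does not support.

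- *Two primary measures give two chances at a false positive.* Step 5 shows almost no inflation at the sparse rates where the results diverge, and about one percentage point at 80 per 1,000. The odds ratio is a separate matter. With 35% against 15% discontinuing and 50 events per 1,000, it rejects a true null in 8.7% of studies (constant hazard), but that is bias from ignoring person-time, cured by dropping it.
- *The sponsor could pick whichever is significant.* At a true ratio of 2, only the averaged result is significant in under 2% of studies.
- *Rate ratios and hazard ratios often contradict each other.* With one stratified fit and constant hazards they rarely do (step 4). With early-clustered events and unequal discontinuation, disagreement was 2.0% to 9.7%.

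**Conclusion.** The point holds as a conflict between stated rules. SAP 4.9.1 differs from SAP 2.1 on which endpoints are primary, and from the protocol and SAP 4.10 on how the incidence rate is analysed. The main harm is an undefined primary result and, if 4.9.1 is followed literally, a less precise one. At 10 to 20 events per 1,000 person-years and a true ratio of 2, the averaged analysis detects the difference in 3% to 31% of studies against 25% to 49%. The loss is small at 40 per 1,000 and negligible at 80.

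These sizes rest on assumed rates, five strata, 0.85 person-years per patient and constant hazards. More strata, which SAP 4.9 allows, would thin events further. The absence of a ranking rule is established only for the readable text. No family-wise error claim should be attached. This should be corrected before analysis, but it does not threaten the study.

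**What to change.** In SAP 4.9.1, state that for each outcome the single primary contrast is the person-time incidence rate ratio, empagliflozin versus DPP-4 inhibitor, in the index period, estimated by Mantel-Haenszel across the PS strata of SAP 4.9. In the same section:

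- remove logistic regression as the primary analysis of incidence rates;
- limit the stratum-averaging and covariate sentences to supportive models;
- report the hazard ratio with its 95% CI as supportive, with no significance claim resting on it.

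Align SAP 2.1, protocol 9.7.2 and the abstract, with one statement of strata and weights. The abstract has deciles, calendar year and empagliflozin person-time weights. Protocol 9.7.2 has quintiles, and SAP 4.9 has quintiles that may be increased. Mantel-Haenszel weights and empagliflozin person-time weights are different estimators, so the text must choose one for the primary contrast.

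Cost: a small wording change in the SAP and the protocol. No listed table is lost, since section 5.1 already plans stratified IRR and proportional-hazards outputs and names no odds-ratio table. The hazard ratio no longer carries a formal claim.

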4.7.5 Ketoacidosis, severe UTI, depletion and dehydration

As main endpoints, ketoacidosis, severe UTI (namely pyelonephritis and urosepsis), volume depletion and dehydration, will be derived from corresponding AE reporting. Crude and treatment-adjusted incidence rates will be presented by group and period, together with incidence rate ratios of EMPAGLIFLOZIN relative to DPP-4 inhibitor, as point estimates and with 95% confidence limits. Treatment-adjusted incidence rates are defined as crude incidence rates per 1,000 person-years. Per group, and, where appropriate, per stratum and/or subgroup, the number of person-years is the sum of length of index periods of all respective patients.

For each endpoint, the time from index date to first occurrence in days is determined. If the endpoint does not occur for a patient, the time is right-censored by the duration of the respective period, index period or follow-up period. By group, times to first occurrence will be described by means of Kaplan-Meier estimates with 95% confidence limits and, where appropriate, median times with 95% confidence limits.

Crude and treatment-adjusted incidence rates and respective incidence rate ratios will be described in summary tables by group and period, and per period in subgroups by metformin status, GLD status and insulin status, respectively. Ratios are defined as Empagliflozin to DPP-4 inhibitors.

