albuterol, dopamine, dobutamine, terbutaline and ritodrine. However, candidates cannot be considered if unknown or missing in a significant number of patients.

If the p-value of bivariate analysis is lower than 0.25, confounder candidates will be included in an initial multivariate logistic regression model. By backward elimination, or other appropriate methods of model selection, the model will be optimized to yield a final model.

The resulting PS will be described by group by means of a summary table. The distribution of the PS will be plotted for the two treatment groups (EMP, DPP-4 inhibitors) to see whether there are any areas where there is no overlap. The estimates of treatment effect may not be reliable in areas where there is no overlap. The area with overlap is called the common support region. It may be necessary to remove subjects outside of the common support region (e.g. extreme tails of the PS distribution) before analysis.

The effect of the confounders in bivariate testing and in the initial and final models will be described by p-values.

PS-based Analysis

Based on those PS, the main analysis approach is stratification to control for confounders,

The stratification will divide the entire study population into five groups by PS quintiles based on their PS value. Quintiles will be used for analysis if the number of patients are sufficiently balanced per group within strata and if the confounding covariates are balanced. Balance will be reviewed graphically and, depending on the scale of the covariate, by Mantel-Haenszel and other applicable tests of confounding covariates of the final model by strata. If, due to significantly low p-values from Mantel-Haenszel and other applicable tests, the balance based on quintiles is insufficient, the number of strata will be increased. Balance investigations will be repeated and the number of strata further increased until a reasonable degree of balance is achieved. It may also be necessary to remove patients from extreme tails of the PS distribution.

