4.9.2 Analysis of Secondary Endpoints

Secondary endpoints are the same as primary endpoints but in the index period during Ramadan. They are analyzed like the primary endpoints.

Statistical Analysis Plan (SAP)

Document Date: 17APR2019

Document Version: 1.0 Final

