4.10 Changes From Protocol-Specified Analyses

As planned per protocol, stratified Mantel-Haenszel analysis will be applied to evaluate incidence rates of each of the target AEs. 

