15.17	Diabetic Ketoacidosis: PS Confounders Summary – Standardized Differences and p-values
15.18	Diabetic Ketoacidosis: Stratified IRR Analyses, Index Period
15.19	Diabetic Ketoacidosis: Stratified IRR Analyses, Index Period during Ramadan
15.20	Diabetic Ketoacidosis: Stratified IRR Analyses, Follow-up Period
15.21	Diabetic Ketoacidosis: Stratified IRR Analyses, Follow-up Period during Ramadan
15.22	Diabetic Ketoacidosis: Stratified PH Analyses of Time to First Occurrence in Index Period
15.23	Diabetic Ketoacidosis: Stratified PH Analyses of Time to First Occurrence in Index Period during Ramadan
15.24	Diabetic Ketoacidosis: Stratified PH Analyses of Time to First Occurrence in Follow-up Period
15.25	Diabetic Ketoacidosis: Stratified PH Analyses of Time to First Occurrence in Follow-up Period during Ramadan
16.1-25	same 25 outputs for severe UTI
17.1-25	same 25 outputs for volume depletion
18.1-25	same 25 outputs for dehydration

Statistical Analysis Plan (SAP)

Document Date: 17APR2019

Document Version: 1.0 Final

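### SAP 4.9.1 analyses the primary incidence rates by averaging per-stratum logistic regressions, while the protocol, SAP 4.10 and the planned tables call for a person-time Mantel-Haenszel IRR; averaged log odds ratios would often have no finite value for rare events

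*SAP*

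**What the plan says.** **SAP 4.9.1** makes incidence rates and times to first occurrence in the index period the primary endpoints, "analysed within each PS-based stratum by logistic regression and proportional-hazards Cox regression, respectively". It continues: "Estimates for each stratum and respective variances will be averaged across strata to yield overall weighted estimates considering subclass weights". The scale of the averaging is not named. The models "will include the season, i.e., the quarter of the calendar year of the index date", and may include other covariates. **SAP 4.9.2** says of the Ramadan endpoints: "They are analyzed like the primary endpoints".

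**Protocol 9.7.2** investigates IRRs by a stratified Mantel-Haenszel analysis over PS quintiles, on person-years summed over index periods, with follow-up censored when the index drug is stopped or switched. **SAP 4.7.5** uses the same denominator: "the number of person-years is the sum of length of index periods of all respective patients". **SAP 4.10** says: "As planned per protocol, stratified Mantel-Haenszel analysis will be applied to evaluate incidence rates of each of the target AEs"; the text after that sentence is blacked out, and section 4.9.3 is not shown. **SAP 5.1** lists tables such as "Diabetic Ketoacidosis: Stratified IRR Analyses, Index Period" and proportional-hazards tables, but none for odds ratios.

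The strata vary too. The protocol abstract uses PS deciles by calendar year, protocol 9.7 at most five groups, and protocol 9.7.2 quintiles. SAP 4.9 starts with quintiles and sets no upper limit: "Balance investigations will be repeated and the number of strata further increased until a reasonable degree of balance is achieved". Protocol 9.3.2 also requires stratification by calendar time of treatment initiation.

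**The concern.** A programmer following SAP 4.9.1 produces an odds ratio and cannot fill the IRR tables from it. One following SAP 4.10 produces an IRR. In the readable text nothing says which is the primary rate comparison, so the choice could be made after the results are known.

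The two methods also behave differently.

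- **Person-time.** Logistic regression counts patients with an event and ignores time at risk. With censoring at stopping, unequal stopping between cohorts biases the odds ratio as a substitute for the IRR. The Cox models do use time at risk.
- **Sparse events.** A stratum with no event in one cohort has no finite log odds ratio or log hazard ratio and no usable variance. An average over strata therefore needs events in both cohorts of every stratum. Mantel-Haenszel sums over strata before dividing, so it needs only one event per cohort overall. Protocol 7 calls ketoacidosis rare, and protocol 9.9 concedes that numbers may be low. The rule for adding strata looks only at covariate balance, not at event counts.

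**Working it through.** **Inputs.** 1,500 patients, with 750 per cohort as the aim (protocol 9.5, SAP 4.2); 2 × 750 = 1,500. The size is set by the regulator with no rate, effect or power, so there is no further figure to reproduce. Five strata (SAP 4.9). Follow-up of at most 12 months, so at most about 750 person-years (PY) per cohort. Assumed: a full year for everyone, equal rates r, and cohorts split evenly in each stratum, giving 10 cells of 150 PY. Event counts are taken as Poisson.

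**Probability that an estimate exists.**

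- Average of log odds ratios (or log hazard ratios) from ordinary maximum likelihood: (1 − exp(−150r))^10.
- Mantel-Haenszel (MH) IRR finite and non-zero: (1 − exp(−750r))^2.

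| Rate per 1,000 PY | Average | MH IRR |
|---|---|---|
| 1 | near 0 | 28% |
| 5 | 0.528^10 = 0.2% | 0.976^2 = 95% |
| 10 | 0.777^10 = 8% | 99.9% |
| 20 | 60% | about 100% |
| 35 | 95% | about 100% |

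**50% points.** Average: r = −ln(1 − 0.5^0.1)/150 = 18.0 per 1,000 PY, about 27 events in total. MH: r = −ln(1 − 0.5^0.5)/750 = 1.6 per 1,000 PY. A simulation of 200,000 replicates gave 49.9% for the average at 18. Covariates such as season cannot rescue a stratum that has no event in one cohort.

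**Sensitivity of the 18 (mean rate over both cohorts).**

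- 40% against 20% stopping (assumed; 611 and 684 PY with the 30-day grace): 21.0. At 18 the average is then finite 36% of the time.
- Empagliflozin share running from 20% to 80% across strata (assumed): 25.5. At 18, finite 25% of the time.
- Rate ratio of 2: 21.4 (a comparator rate of 14.3).
- Ten strata: 45.1.

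With five strata, each departure raises the break-even mean rate, so 18 is a floor.

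**Ramadan.** SAP 2.2 counts 29 days; the end dates in SAP 4.4 give up to 33. PY per cohort = 750 × 29/365.25 = 59.5 to 750 × 33/365.25 = 67.8, if everyone contributes. The 50% points are 227 to about 200 per 1,000 PY for the average, and 1.228/59.5 = 20.6 to 1.228/67.8 = 18.1 for MH.

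**Person-time.** With stopping probability d in the year, h = −ln(1 − d), and grace g in years, mean person-time is g + (1 − exp(−h(1 − g)))/h. For a rare event and a true IRR of 1, the odds ratio is about the ratio of mean person-times.

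- 40% against 20% stopping (assumed), no grace: 0.783/0.896 = 0.87. With 30 days: 0.815/0.912 = 0.89. If the cohorts swap: 1.14 and 1.12.
- 30% against 20%: 0.94 to 0.95.

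For comparison, the 95% interval factor exp(1.96 × √(2/(750r))) is 4.2 at 5 and 1.6 at 50 per 1,000 PY.

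**The abstract's weighting.** It weights stratum incidences or IRRs by empagliflozin person-time. Averaging IRRs needs a comparator event in every stratum: (1 − exp(−150r))^5 = 4% at 5 and 28% at 10 per 1,000 PY. Weighting incidences and then taking their ratio works as often as MH, 95% and 99.9%.

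**Calendar time.** In a simulation of 40,000 runs with quintiles by two index years (split 1/3 to 2/3, assumed), the MH IRR was finite in 95% and 99.9% of runs at 5 and 10 per 1,000 PY. The SD of the log IRR at 10 was unchanged at 0.58.

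**The case against.** The strongest reply is that the plan may already settle this where it cannot be read. SAP 4.10 exists to reconcile SAP and protocol, its one readable sentence keeps Mantel-Haenszel, and 4.9.3 is not shown. With only IRR tables planned for the rates, one can argue that the IRR is what will be reported and that a single sentence in 4.9.1 is loosely worded. This stands to a point: a reader might infer that the SAP has no ranking of methods and no rule for empty strata, and the documents do not support that. The conflict in the readable text of 4.9.1 remains.

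Other inferences also go too far.

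- *The primary ketoacidosis estimate will fail.* No ketoacidosis rate is given. The failure also depends on averaging log ratios from unpenalised fits. If stratum risks were averaged, a penalised fit used, or infinite-variance strata given no weight, it would not occur. SAP 4.9.1 specifies subclass weights and no penalised method, but leaves the scale open.
- *Above 18 per 1,000 PY the problem is gone.* 18 is a best case.
- *The abstract's weighting fails as well.* Only its IRR reading does.
- *The odds ratio is badly inflated at the 25% in protocol 9.5.* That figure is a prevalence of urinary tract infection and other risk factors, not an incidence of severe infection, so it supports no such calculation.

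It is also fair that Mantel-Haenszel is no full cure: at 1 per 1,000 PY it gives a usable ratio only 28% of the time.

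**Conclusion.** The concern holds as a conflict in the readable text. SAP 4.9.1 prescribes stratum-wise logistic regression with averaging for a quantity that protocol 9.7.2, SAP 4.7.5, SAP 4.10 and the table list treat as a person-time IRR. It should be fixed.

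Its size depends on the outcome rate and on the averaging scale. If log ratios from ordinary fits are averaged, then under the most favourable layout the average more likely than not does not exist below about 18 per 1,000 PY (mean rate 21 to 25.5 under the less even layouts tried). The MH IRR more likely than not exists down to about 1.6. Below that both usually fail. Whether ketoacidosis lies in this range cannot be read from the documents. For the Ramadan endpoints the gap is wider, about 200 to 227 against 18 to 21 per 1,000 PY.

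The person-time bias is systematic if stopping differs between cohorts, but small beside sampling error for rare events. Crude rates, crude IRRs and Kaplan-Meier estimates are not affected.

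**What to change.** In SAP 4.9.1 and 4.9.2, before outcome data are analysed:

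- Make the person-time Mantel-Haenszel IRR over PS strata the primary rate comparison, replacing the per-stratum logistic regression and averaging. Ensure that 4.10 agrees.
- Use exact conditional confidence intervals when events are sparse. State the event count at which this applies, or use them throughout.
- If one cohort has no events, report only the exact one-sided bound. If neither has, report no ratio and give each cohort's exact upper limit; with 0 events in 750 PY this is −ln(0.025)/750 = 4.9 per 1,000 PY (two-sided 95%).
- Estimate the hazard ratio from one Cox model stratified by PS stratum with a common treatment coefficient, reported as not estimable if a cohort has no events.
- Keep calendar time of initiation as a stratifier in both analyses, for example index year. The protocol abstract and 9.3.2 stratify by it, and in the readable SAP only the season term in the 4.9.1 models carries it. Putting it in the PS model alone would not meet that wording.
- Reconcile the strata (deciles by calendar year, at most five groups, quintiles, no upper limit) and say whether the abstract's weighting applies to incidences or to IRRs.

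The cost is SAP wording, simpler programming and a protocol clarification for the abstract. The downside is less outcome-model covariate adjustment beyond the PS and calendar time.
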